While it can be a challenge to specify the details of the research that will be conducted in the future, the I-PWG holds the view that future use of samples collected for exploratory biomarker research in clinical trials should be permissible when i) the research is scientifically sound, ii) participants are informed of the scope of the intended future research, even if this is broadly defined (see potential uses in Section 4 above), iii) autonomy is respected by providing the option to consent separately to future use of samples or by providing the option to terminate further use of samples upon request (consent withdrawal / sample destruction), and iv) industry standards for confidentiality protection per Good Clinical Practice guidelines are met.²⁹⁻³¹ Importantly, any research using banked samples should be consistent with the original informed consent, except where otherwise permitted by local law or regulation.

Important elements of informed consent for **future use** of samples include, but are not limited to:³⁰

The scope of research – Where the scope of the potential future research is broad, participants should be informed of the boundaries of the research. While it may not be possible to describe the exact analytical techniques that will be used, or specific molecules that will be analyzed, it is possible to clearly articulate in reasonable detail the type of research to be conducted and its purpose. Information regarding whether stored samples may be shared with other parties or utilized for commercialization purposes should also be addressed.

Withdrawal of consent / sample destruction – The informed consent form should inform participants of their right to withdraw their consent / request destruction of their samples. This should include the mechanisms for exercising that right and any limitations to exercising that right. For example, participants should be informed that it is not possible to destroy samples that have been anonymized.³¹ In addition, according to industry standards and regulatory guidance, participants should be informed that data already generated prior to a consent withdrawal request are to be maintained as part of the study data.³⁰

The duration of storage – The permissible duration of storage may vary according to the nature and uses of the samples and may also vary on national, state, and local levels. The intended duration of storage, including indefinite storage, should be specified.

8. Biomarker Sample Collection in Different Countries

Collection of biological samples for biomarker research is straightforward in most jurisdictions. Some countries have specific laws and regulations regarding collection, labeling, storage, export, and/or use of exploratory samples. In addition, some regulations distinguish between DNA and non-DNA samples or between samples used for diagnostic purposes and samples collected for scientific research. Processes for the collection, labeling, storage, export, and/or use of biomarker samples should always adhere to the laws and regulations of the country/region in which those samples are collected.

9. Return of Research Results to Study Participants

Policies for the return of biomarker research results to study participants who request them vary among pharmaceutical companies. There are many considerations that pharmaceutical companies weigh when determining their policy regarding the return of biomarker research results to study participants. These include:

- i) the conditions under which biomarker research results were generated (i.e., exploratory research laboratory versus accredited diagnostic laboratory)
- ii) whether the results will have an impact on the medical care of the participant or on a related person, if applicable
- iii) whether genetic counseling is recommended (for genetic results)
- iv) the ability to accurately link the result to the individual from whom the sample was collected
- v) international, national, and local guidelines, policies, legislation, and regulations regarding participants' rights to access data generated on them

Renegar *et al.* 2008 and Article 29 Data Protection Working Party (an advisory committee to the European Commission on the European Data Protection Directive) have addressed these considerations in detail in relation to pharmacogenomic research data and provided a list of documents addressing the general issue of return of research results.²⁴⁻²⁶

10. Benefits and Risks Associated with Biomarker Research

Benefits

While it may not always directly benefit the study participant who is providing the samples, biomarker research can improve overall understanding of disease and treatment of future patients receiving therapies developed from such research. Patients are now benefiting from retrospective biomarker research conducted on samples collected from clinical trials and stored for exploratory research. One example is the recent label update to the EGFR antibody drugs cetuximab (Erbix[®]) and panitumumab (Vectibix[®]) which highlights the value of KRAS status as a predictive biomarker for treatment of metastatic colorectal cancer with this class of drug.

The humanitarian benefit of human research is recognized by the Nuremberg Code.^{28,29} Provided that the degree of risk does not exceed that determined by the humanitarian importance of the problem to be solved, research participants should not be denied the right to contribute to the greater common good.^{28,32}

Risks

Risks associated with biomarker research are primarily related to the physical aspects of obtaining the sample and to patient privacy concerns.

Physical risks associated with biomarker sample collection in clinical trials can be characterized in two ways: i) negligible additional risk when the biomarker sample is collected as part of a procedure conducted to support

other core trial objectives, and ii) some added risk where the sampling procedure would otherwise have not been performed as a core component of a trial. Risks are also determined by the invasiveness of the sample collection procedure.

Privacy risks are generally those associated with the inappropriate disclosure and misuse of data. Pharmaceutical companies have policies and procedures for confidentiality protection to minimize this risk for all data collected and generated in clinical trials. These may vary across companies, but are based on industry standards of confidentiality and privacy protection highlighted in the following section. Importantly, privacy risks inherent to biomarker data are no greater than other data collected in a clinical trial.

11. Privacy, Confidentiality, and Patient Rights

Maintaining the privacy of study participants and the confidentiality of information relating to them is of paramount concern to industry researchers, regulators, and patients. Good Clinical Practice (GCP), the standard adhered to in pharmaceutical clinical research, is a standard that

... provides assurance that the data and reported results are credible and accurate, and that the rights, integrity, and confidentiality of trial subjects are protected.

where confidentiality is defined as, *"The prevention of disclosure, to other than authorized individuals, of a sponsor's proprietary information or of a subject's identity."*

This standard dictates that *"the confidentiality of records that could identify subjects should be protected, respecting the privacy and confidentiality rules in accordance with applicable regulatory requirements."*²¹

[figure not shown]
Exploratory biomarker research in pharmaceutical development is commonly conducted in research laboratories that are not accredited to perform diagnostic tests used for healthcare decision-making. Therefore, results from exploratory biomarker research usually are not appropriate for use in making decisions about a trial participant's health. In addition, exploratory research data should not be included as part of a participant's medical record accessible for use by insurance companies. Legislation and policies to protect individuals against discrimination based on genetic information continually evolve based on social, ethical, and legal considerations. Examples of such legislation include the Human Tissue Act 2004 (UK) and the Genetic Information Nondiscrimination Act (GINA) 2008 (USA).²⁶⁻²⁷

12. Where to Get More Information?

Educational resources related to biomarker and pharmacogenomic research that caters to health care professionals, IRBs/IECs, scientists, and patients are continually being created and are publicly available. Links to many of these resources are available through the I-PWG website: www.i-pwg.org.

13. What is I-PWG?

The Industry Pharmacogenomics Working Group (I-PWG) (formerly the Pharmacogenetics Working Group) is a voluntary association of pharmaceutical companies engaged in pharmacogenomic research. The Group's activities focus on non-competitive educational, informational, ethical, legal, and regulatory topics. The Group provides information and expert opinions on these topics and sponsors educational/informational programs to promote better understanding of pharmacogenomic and other biomarker research for key stakeholders. The I-PWG interacts with regulatory author-

ities and policy groups to ensure alignment. More information about the I-PWG is available at: www.i-pwg.org.

14. Contributing authors

12.4 ECOG Performance Status

Grade	Description
0	Normal activity. Fully active, able to carry on all pre-disease performance without restriction.
1	Symptoms, but ambulatory. Restricted in physically strenuous activity, but ambulatory and able to carry out work of a light or sedentary nature (e.g., light housework, office work).
2	In bed <50% of the time. Ambulatory and capable of all self-care, but unable to carry out any work activities. Up and about more than 50% of waking hours.
3	In bed >50% of the time. Capable of only limited self-care, confined to bed or chair more than 50% of waking hours.
4	100% bedridden. Completely disabled. Cannot carry on any self-care. Totally confined to bed or chair.
5	Dead.
* As published in Am. J. Clin. Oncol.: Oken, M.M., Creech, R.H., Tormey, D.C., Horton, J., Davis, T.E., McFadden, E.T., Carbone, P.P.: Toxicity And Response Criteria Of The Eastern Cooperative Oncology Group. Am J Clin Oncol 5:649-655, 1982. The Eastern Cooperative Oncology Group, Robert Comis M.D., Group Chair.	

12.5 Common Terminology Criteria for Adverse Events (CTCAE) version 4.0

The descriptions and grading scales found in the revised NCI Common Terminology Criteria for Adverse Events (CTCAE) version 4.0 will be utilized for adverse event reporting. (<http://ctep.cancer.gov/reporting/ctc.html>).

12.6 Response Evaluation Criteria in Solid Tumors (RECIST) 1.1 Criteria for Evaluating Response in Solid Tumors

RECIST version 1.1* will be used in this study for assessment of tumor response. While either CT or MRI may be utilized, as per RECIST 1.1, CT is the preferred imaging technique in this study.

* As published in the European Journal of Cancer [32].

12.7 Dose Modification Table (based on modified Toxicity Profile Interval [33])

Sample size = 18^a; Target probability $p_T = 30\%$; $\epsilon_1 = \epsilon_2 = 0.05$.

Any doses with a dose reduction probability falling into the interval $(p_T - \epsilon_1, p_T + \epsilon_2)$ will be considered an acceptable dose level.

		Number of Patients																	
		1	2	3	4	5	6	7	8	9	10	11	12	13	14	15	16	17	18
Number of Toxicity	0	E	E	E	E	E	E	E	E	E	E	E	E	E	E	E	E	E	E
	1	D	S	S	S	S	E	E	E	E	E	E	E	E	E	E	E	E	E
	2		D	D	S	S	S	S	S	S	S	E	E	E	E	E	E	E	E
	3			D	D	D	S	S	S	S	S	S	S	S	S	E	E	E	E
	4				D	D	D	D	D	S	S	S	S	S	S	S	S	S	S
	5					D	D	D	D	D	S	S	S	S	S	S	S	S	S
	6						D	D	D	D	D	D	D	S	S	S	S	S	S
	7							D	D	D	D	D	D	D	D	S	S	S	S
	8								D	D	D	D	D	D	D	D	D	D	S
	9									D	D	D	D	D	D	D	D	D	D
	10										D	D	D	D	D	D	D	D	D
	11											D	D	D	D	D	D	D	D
	12												D	D	D	D	D	D	D
	13													D	D	D	D	D	D
	14														D	D	D	D	D
	15															D	D	D	D
	16																D	D	D
	17																	D	D
	18																		D

LEGEND

E: Stay at same dose or escalate to the next higher dose (escalation will only apply if the initial dose has been lowered, as doses higher than 800 mg/m² for 5-FU, 1000 mg/m² twice daily for capecitabine (Japan only) and 80 mg/m² for cisplatin will not be studied); **S**: Stay at the same dose; **D**: De-escalate to a lower dose;

a. Subjects enrolled at Asian sites and non-Asian sites will be assessed separately. If the dose level for one subgroup has been lowered while the other remains at the higher starting dose, then consideration may be made to increase the dose back to the starting dose based on tolerability in the individual subgroup and the overall population across subgroups.

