[figure not shown]

Figure 2 Cohort 2 –1L Combination Treatment

Approximately 18 subjects, regardless of PD-L1 status, will be enrolled in Cohort 2 and receive pembrolizumab as 1L therapy in combination with cisplatin+5-FU or cisplatin+capecitabine (Figure 2). A total of 6 subjects in Japan will be administered capecitabine instead of 5-FU. Approximately 12 subjects in Cohort 2 will be enrolled by sites in Asia. Approximately 6 subjects will be enrolled by sites outside of Asia. Every effort will be made to adhere to the regional or country subject allocation identified here.

Cohort 3 subjects will receive pembrolizumab as 1L monotherapy (Figure 3).

[figure not shown]

Figure 3 Cohort 3 –1L Monotherapy

Approximately 25 PD-L1 positive subjects will be enrolled in Cohort 3 and receive pembrolizumab as 1L monotherapy (Figure 3). Enrollment into Cohort 3 is contingent on the availability of the PD-L1 assay.

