5.2.1.2.2 Guidelines for Dose Modification Due to Adverse Events

The Common Terminology Criteria for Adverse Events version 4.0 (CTCAE 4.0) must be used to grade the severity of adverse events.

If appropriate, the investigator may attribute each toxicity event to any of the individual chemotherapy agents used or pembrolizumab alone in the combination arms and use stepwise dose modifications according to [Table 3](#). Pembrolizumab dose reductions are not permitted. Pembrolizumab treatment may be interrupted or discontinued due to toxicity. If a dose level reduction for toxicity occurs with any agent, the dose may not be re-escalated. Dose modifications are always based on the previous cycle.

Dose modification for cisplatin + 5-FU or capecitabine combination are detailed in [Table 3](#). Subjects may have up to 2 dose level reductions per chemotherapy agent throughout the course of the study ([Table 3](#)). If further toxicity occurs or the criteria for resuming treatment are not met, the subject must be discontinued from chemotherapy treatment. Of note, in the event a subject in Cohort 2 is discontinued from chemotherapy treatment, the subject may still be eligible for continued treatment with pembrolizumab (DL -3 in [Table 3](#)). Refer to [Table 4](#), [Table 6](#), and [Table 7](#), for dose modification guidelines for AEs related to pembrolizumab, cisplatin, 5-FU, and capecitabine (Japan only), respectively. If a subject experiences several toxicities and there are conflicting recommendations, follow the most conservative dose adjustment recommended (dose reduction appropriate to the most severe toxicity).

Reduction or with-holding of one chemotherapy agent and not the other agent is appropriate if, in the opinion of the investigator, the toxicity is clearly related to one of the study treatment. If, in the opinion of the investigator, the toxicity is related to the

combination of 2 chemotherapy agents, both treatments should be reduced (if applicable), interrupted or discontinued according to recommended dose modifications. If the toxicity is related to the combination of 3 agents, all three agents should be reduced or held according to the recommended dose modifications.

Exceptional circumstances to following the dose modification tables below may be considered after consultation with the Sponsor.

Table 3 Dose Modifications for Trial Medication

	Starting Dose	Dose Level -1	Dose Level -2	Dose Level -3

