Pembrolizumab	200 mg fixed dose	Dose reductions are not permitted	Dose reductions are not permitted	Dose reductions are not permitted
Cisplatin	80 mg/m ²	60 mg/m ²	40 mg/m ²	Discontinue
5-FU	800 mg/m ²	600 mg/m ²	400 mg/m ²	Discontinue
Capecitabine (Japan Only)	1000 mg/m ² BID	750 mg/m ² BID	500 mg/m ² BID	Discontinue

If a toxicity is not otherwise specified, investigators should refer to the label or local standard of care for dose adjustments. At the investigator's discretion, dose modification according to [Table 3](#) is allowed for intolerable Grade 2-3 toxicities that are not specified in the tables below. These dose modification decisions must be documented in the subject's study records.

In Cohort 2, the number of treated subjects versus the number of subjects with a dose reduction will be monitored continuously. Appendix 12.7 provides guidance for determination of lowering the dose for the chemotherapy agents for a treatment subgroup (i.e., Asian or non-Asian) according to a mTPI method.

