5.2.1.2.6 Dose Modifications for 5-FU/Capecitabine

Please refer to criteria for 5-FU and capecitabine dose modification included in [Table 7](#).

Table 7 Dose Modification Guidelines for 5-FU/Capecitabine Drug-Related Adverse Events

Category	Toxicity	Hold 5-FU/ capecitabine ³ Treatment for Grade	Timing for Restarting 5- FU/ capecitabine ³ Treatment	Dose for Restarting 5-FU/ capecitabine ³ Treatment	Discontinue 5-FU/ capecitabine ³
Hematologic	Neutropenia	3 ¹	Neutrophil count resolves to >1,000/mm ³	No Reduction *consider G-CSF	Toxicity does not resolve within 12 weeks of last infusion or if >-2 DL reductions exceeded
		4 ¹	Neutrophil count resolves to >1,000/mm ³	Reduce by 1 DL *consider G-CSF	Toxicity does not resolve within 12 weeks of last infusion or if >-2 DL reductions exceeded
	Febrile Neutropenia	3 ¹	Toxicity resolves to Grade 0-1	Reduce by 1 DL	Toxicity does not resolve within 12 weeks of last infusion or if >-2 DL reductions exceeded
		4 ¹	n/a	Discontinue	Permanently discontinue 5-FU/capecitabine.
	Thrombo- cytopenia	3-4 ¹	Platelet count resolves to >75,000/mm ³	Reduce by 1 DL	Toxicity does not resolve within 12 weeks of last infusion or if >-2 DL reductions exceeded
Non- hematologic	Diarrhea, Mucositis, or Hand-foot syndrome	2-3	Toxicity resolves to Grade 0-1	Reduce by 1 DL	Toxicity does not resolve within 12 weeks of last infusion or if >-2 DL reductions exceeded
		4	n/a	Discontinue	Permanently discontinue 5-FU/capecitabine.
	All other non- hematologic toxicities ²	3-4 ¹	Toxicity resolves to Grade 0-1	Reduce by 1 DL	Toxicity does not resolve within 12 weeks of last infusion or if >-2 DL reductions exceeded
	Laboratory Adverse Events	4 ¹	Toxicity resolves to Grade 0-1	Reduce by 1 DL	Toxicity does not resolve within 12 weeks of last infusion or if >-2 DL reductions exceeded

¹Permanent discontinuation should be considered for any severe or life-threatening event. Consult Sponsor before restarting treatment after Grade 4 drug related AE.

²Subjects with intolerable or persistent Grade 2 drug-related AE may hold at physician discretion. Permanently discontinue from agent for persistent Grade 2 adverse reactions for which treatment has been held, and did not recover to Grade 0-1 within 12 weeks of the last dose.

³ Capecitabine applicable to sites in Japan

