Cohort 2 (1L gastric cancer subjects/combination treatment): There will be approximately 18 subjects enrolled for all-comer population. [Table 17](#) shows the two-sided 95% CI of AE rate with 18 subjects.

Table 17 Two-sided 95% CI of AE incidence rate with 18 Subjects

Number of AE	AE incidence rate estimates	95% CI of incidence rate (%)
2	11.1%	(1.4, 34.7)
4	22.2%	(6.4, 47.6)
5	27.7%	(9.7, 53.5)
7	38.9%	(17.3, 64.2)
9	50.0%	(26.0, 73.9)

Cohort 3 (1L gastric cancer subjects/monotherapy): There will be ~25 PD-L1 positive subjects enrolled in Cohort 3. Using Bayesian sample size methods and assuming a uniform prior for the response rate (beta-binomial prior with beta (1, 1)), if we observe no more than 8 responders (i.e. observed ORR \leq 32%), there is \geq 77% posterior probability that the true ORR is less than 40% (ORR from Standard of Care).

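### Two of the 189 cells in the Cohort 2 mTPI table (Appendix 12.7) do not follow from its stated inputs; only 5/10, printed S where the rule gives D, can matter at the planned subgroup sizes

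*Combined protocol and SAP*

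**What the plan says.** Section 5.2.1.2.2 of the protocol says that in Cohort 2 "the number of treated subjects versus the number of subjects with a dose reduction will be monitored continuously", and refers to Appendix 12.7 for guidance on when to lower the chemotherapy dose for a regional subgroup.

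The appendix names the modified toxicity probability interval method, sets a target of 30% with both epsilons at 0.05, and prints E, S or D for every count of events in 1 to 18 patients. "Any doses with a dose reduction probability falling into the interval" around the target are called acceptable. Under the legend, E means stay, or escalate if the dose was lowered earlier; S means stay; D means de-escalate.

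Footnote a of the appendix adds: "Subjects enrolled at Asian sites and non-Asian sites will be assessed separately". Section 2.2 gives the sizes: "Approximately 12 subjects in Cohort 2 will be enrolled by sites in Asia", and about 6 elsewhere.

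The two cells at issue are 5 events in 10 subjects, printed S, and 3 events in 15, printed E.

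**The concern.** Once the method, target, epsilons and prior are fixed, every cell is determined. The printed table is also inconsistent with itself. At an observed rate of 50% it gives D at 4/8, S at 5/10, and D again at 6/12 and 7/14. More data at the same rate, well above target, should not relax the decision and then tighten it again.

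At 5/10 the table tells the team to hold the chemotherapy dose when half the subjects have needed a reduction against a 30% target. Section 4.2.1.2 says doses may be lowered for a whole cohort and that the experience will inform dosing in later combination trials, so the thresholds have a use beyond this cohort.

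**Working it through.** **Inputs.** Target 0.30 and epsilons 0.05 (Appendix 12.7), giving intervals E (0, 0.25), S (0.25, 0.35) and D (0.35, 1). Printed cells come from the same appendix. Subgroup sizes of about 12 and 6 come from Section 2.2. The prior is assumed to be Beta(1,1). The appendix states none, but Section 8.9 works on the same footing for Cohort 3, "assuming a uniform prior for the response rate".

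**Rule.** With x events in n subjects the posterior is Beta(1+x, 1+n−x). The unit probability mass (UPM) of an interval is its posterior probability divided by its length (0.25, 0.10 and 0.65). The interval with the largest UPM gives the decision.

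**Reproducing the table.** There are 189 cells (the sum of n+1 for n = 1 to 18). The rule reproduces 187 of them; only 5/10 and 3/15 differ.

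**The two cells.**

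- 5/10, posterior Beta(6,6): E 0.0343/0.25 = 0.137; S 0.1144/0.10 = 1.144; D 0.8513/0.65 = 1.310. Rule D, printed S.
- 3/15, posterior Beta(4,13): E 0.5950/0.25 = 2.380; S 0.2711/0.10 = 2.711; D 0.1339/0.65 = 0.206. Rule S, printed E.

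Neither is a near tie.

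**Neighbours at a 50% rate.**

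| Cell | UPM S | UPM D | Rule | Printed |
|---|---|---|---|---|
| 4/8 | 1.228 | 1.274 | D | D |
| 5/10 | 1.144 | 1.310 | D | S |
| 6/12 | 1.052 | 1.339 | D | D |
| 7/14 | 0.959 | 1.364 | D | D |

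The margin for D grows with n, so 5/10 lies between two cells that are correctly D.

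**Does another prior explain it?** With the stated target and epsilons, Beta(a,b) was tried with a and b each from 0.1 to 3.0 in steps of 0.1 (900 priors). The fewest mismatches is 2, reached by Beta(1,1) among others and always in the same two cells. No prior gives D at 4/8, S at 5/10 and D at 6/12.

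**Does another rule or target explain it?** Adding an overdose cut-off of 0.95 leaves the same two mismatches; 0.90 gives 5. Raw interval mass gives 48 and mTPI-2 gives 31. Moving the target to 0.32 clears these two cells but creates two others (4/8 and 8/17), and contradicts the stated 30%.

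**How often would 5/10 be reached?** Assume a look after each subject, with outcomes known in order. Because 5/9 and 4/8 are printed D, the only D-free approach is 3/8, 4/9, 5/10. The chance is K·p⁵(1−p)⁵, where K is the number of orderings of 3 events in the first 8 subjects that meet no printed D.

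- Looks from subject 6: K = C(8,3) = 56.
- Looks from subject 1: the first subject must be event-free, with at most 1 event by subject 3 and at most 2 by subject 5. Counting by 0, 1 or 2 events among subjects 2 to 5, K = 1·1 + 4·3 + 5·3 = 28.

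| True rate p | p⁵(1−p)⁵ | From subject 1 (×28) | From subject 6 (×56) |
|---|---|---|---|
| 0.30 | 0.000408 | 1.1% | 2.3% |
| 0.40 | 0.000796 | 2.2% | 4.5% |
| 0.50 | 0.000977 | 2.7% | 5.5% |

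**What follows at 11 subjects.** The printed and correct tables agree again: 5/11 is S and 6/11 is D in both.

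**A smaller wording gap.** Section 5.2.1.2.2 and the appendix sentence count subjects with a dose reduction, while the row axis of the table refers to toxicity. Some events lead straight to discontinuation: Grade 4 febrile neutropenia for both chemotherapy components and, for the fluoropyrimidine, Grade 4 diarrhea, mucositis or hand-foot syndrome (Table 7: "Permanently discontinue 5-FU/capecitabine"). Such a subject can remain in the trial, since "in the event a subject in Cohort 2 is discontinued from chemotherapy treatment, the subject may still be eligible for continued treatment with pembrolizumab". No sentence says whether the subject counts as an event. Table 3 lists discontinuation as Dose Level −3, so counting it is the natural reading.

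**The case against.** The strongest case concerns weight. The table is guidance, not a stopping rule. Individual reductions and discontinuations are governed by Tables 3, 6 and 7 whatever the appendix prints, so a subject with toxicity is still managed. The 3/15 cell lies beyond both planned subgroup sizes, and at the starting dose E and S are the same action because escalation applies only after a reduction. The 5/10 cell is seldom reached. All of that stands and is why the point is minor.

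It may also be said that the error only delays de-escalation by one subject. That is true if the 11th subject has a reduction (6/11 is D). If not, 5/11 is S and the subgroup stays at a dose that the method would already have lowered.

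A second objection is that the appendix writes out neither the UPM rule nor the prior. The rule belongs to the method that the appendix names and cites, agreement in 187 cells confirms it was used, and the D/S/D sequence is not produced by any prior tried. A misprinted or misread letter is possible in a dense grid. However, every row has the right number of entries, and both discrepancies are a run of letters changing one column early, which looks like an error in the table itself.

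Finally, the path probabilities assume that outcomes arrive in order. Under continuous monitoring reductions may arrive late, so the true chance could be lower or higher.

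**Conclusion.** The concern holds as a minor error. Two of 189 printed cells disagree with the stated method. The one that can matter is 5/10, where the threshold for D at 10 subjects is printed as 6 events but should be 5. The error is in the less cautious direction and within reach of the Asian subgroup.

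The chance of meeting it without an earlier D is roughly 1% to 5.5% across the scenarios above. It does not touch the primary adverse event summary. The 3/15 error has no effect at the planned sizes; it could matter only if a subgroup reached 15, or if pooled data were read from the table when re-escalation is considered.

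The exact UPM values rest on the assumed Beta(1,1) prior. The conclusion about 5/10 does not depend on it, given the 900 priors tried. The wording gap is missing detail rather than an error.

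**What to change.** Change 5/10 to D and 3/15 to S; all 189 cells then follow the rule. State the prior used for the table.

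In the same edit, label the row axis as the number of subjects with a dose reduction, and add one sentence saying that permanent discontinuation of a chemotherapy agent for toxicity (Dose Level −3) counts as a reduction.

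The cost is two cells, one label and two short sentences, with no new data and no more patients.
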